## Study Protocol

### Objectives:

*DigiKnowIt News: Teen (DKIN: Teen)* is an interactive educational website designed to educate adolescents (aged 12 to 17) about pediatric clinical research. The main objective of the study is to examine the feasibility of *DKIN: Teen* and its impact on adolescents' knowledge about pediatric clinical trials; self-efficacy about making decisions about participation in clinical research; positive attitudes and beliefs towards participation; and fears related to participating in clinical trials.

### Design:

A small randomized controlled trial design will be conducted online at two time points: 1) baseline/pre-test and 2) post-test (one week after pre-test). The study questionnaires will be programmed into an online data collection system and the intervention itself is also completed online.

Participants will be randomly assigned to one of two conditions: 1) intervention (youth will receive access to *DKIN: Teen* right away) or 2) wait-list control (youth will not have access to the intervention between pre-test and post-test assessments; after completing the post-test questionnaire, youth will be given the option to review *DKIN: Teen*).

### Methods:

*Sample and Recruitment.* Youth between the ages of 12 and 17 will be recruited for the study. To be eligible to participate in the study, the following criteria must be met. Youth in the study must: 1) be between the ages of 12 and 17 years; 2) understand English because the resource and questionnaires are in English; 3) have access to a computer or tablet with internet access for the duration of the study as the intervention and questionnaires are web-based; 4) NOT currently be in or have previously participated in a clinical trial. This study will investigate if the intervention improves attitudes and decision-making of youth who have not yet participated in a clinical trial; thus, excluding those who have already had the experience of being in a clinical trial. Youth will be recruited from across the United States via flyers and a study website in addition to recruitment efforts via Peachjar (digital flyer service used by school districts) and pediatric health organizations and advocacy groups. Efforts will be made to ensure that the intervention and wait-list control groups have about equal amounts of boys and girls as well as healthy youth and youth with varying chronic diseases/disorders and represent diversity in race and ethnicity.

*Procedure.* Parents of interested adolescents will visit the study recruitment website to learn more about the study and respond to the study eligibility screening questions. Parents will be notified onscreen immediately if their child is eligible to participate in the study, and if so, will be given access to online permission and assent forms. They will be instructed to review the forms together so they can decide about participation. Interested participants who decide to complete the forms will be told that in an attempt to have a diverse sample, they may not be

invited to participate. Families can contact the research team about any questions they might have after they have reviewed and signed the forms. Participants and their parents will be instructed to read the permission and assent forms and provide online permission and assent by typing their names into a text box, providing contact information, and clicking a button to indicate permission (parent) or assent (youth), rather than providing a signed hard copy of the forms. They will have the option to download and/or print the forms to retain a copy for their files. Only participants with permission and assent will be permitted to participate in the study. Eligible youth who have assent and have parent permission will be sent an email invitation to participate to their parent by project staff members if there is space for them in the study depending on their demographic characteristics.

Participants will be randomized, stratifying based upon gender (boy/girl/non-binary), race/ethnicity (white/nonwhite), and health status (healthy/chronic illness), to either the intervention group (*DKIN: Teen*) or wait-list control group. A research team member will enroll the participants into their assigned groups using an online study management system. All participants will be assigned a unique ID number that will be associated with their data in place of a name. Parents will receive an enrollment email from the study management system with a link for participating youth to complete the online pretest questionnaire. Next, parents of youth participants in the intervention group will be emailed instructions on how to access *DKIN: Teen*. Youth will be asked to review as much of it as they want within one week. *DKIN: Teen* is expected to take about 1 hour to fully complete and can done in more than one sitting. Project staff members will monitor website usage through a Learning Management System (LMS). Participants in the wait-list control group will receive business-as-usual, which in this case is no information to review about clinical trials.

About one week after completing the pretest, all parents will receive a link for youth participants to access the online posttest. At the end of the posttest, the youth in the intervention group will also receive the Consumer Satisfaction Questionnaire to give feedback about the website. Youth participants in the wait-list control group will have the option of reviewing *DKIN: Teen* after their posttest data have been collected through an email link to their parents. After a week, the wait-list control group will also have the opportunity to complete the Consumer Satisfaction Questionnaire. Parents will receive automatic email reminders from the study management system if their teen has not completed the questionnaires or has not accessed *DKIN: Teen*. The research team will also call a parent or send a check-in email to a parent if there is no response following the automatic reminder. Youth will receive \$20 for the completing the pretest questionnaire and \$30 for completing the posttest via gift cards. At the end of the study, responses on the online questionnaires will be downloaded from the online data collection system and saved on a secure, password-protected network in preparation for statistical analyses.

### *Measures.*

**Knowledge.** This measure has been created for the purposes of this study. Youth will respond to questions that assess their factual knowledge about clinical research (e.g., What is a clinical trial?). Questions are in multiple choice format (some questions have multiple correct answers), and the total score will be calculated.

**Attitudes and Beliefs (adapted from Madsen, Mirza, Holm, Hilsted, & Riis, 2002).** Youth will be asked to respond to questions that assess their positive attitudes about clinical trials (e.g., How do you feel about kids participating in clinical trials?; 1=Not good at all; 2=Not very good; 3=Not sure; 4=Good; 5=Very good) and questions that assess their beliefs about positive aspects of pediatric clinical research (e.g., I believe that clinical trials can help kids; 1=Strongly Disagree; 2=Disagree; 3=Unsure; 4=Agree; 5=Strongly Agree).

**Self-Efficacy (adapted from Bandura, 2006).** Youth will be asked to respond to questions related to their self-efficacy for making decisions related to participation in clinical trials for two areas: 1) gathering information about clinical trials (e.g., Ask my parents questions for more information about clinical trials?); 2) communicating about clinical trials (e.g., Tell the researcher that I don't want to participate in the clinical trial, even if they really want me to do it). Youth will rate each question on a 5-point Likert scale (1 = I cannot do it at all; 5 = I know I can do it). Youth will be asked to respond to additional items to measure youths' confidence for participating clinical trials (e.g., I know what rights I have in a clinical trial. I know whom to ask if I need more information about a clinical trial.; 1=Strongly Disagree; 2=Disagree; 3=Unsure; 4=Agree; 5=Strongly Agree).

**Procedural fears (adapted from Kowalsky, France, France, Whitehouse, & Himawan, 2014).** Youth will be asked to respond to questions related to their perceptions of fear or anxiety about different types of medical procedures, including getting a needle in the arm, injection in the leg, getting a scan, and taking new medicine, on a 5-point Likert scale (1 = Not at all afraid or anxious, 2 = Somewhat afraid or anxious, 3 = Moderately afraid or anxious, 4 = Very afraid or anxious, 5 = Extremely afraid or anxious).

**Fidelity of Implementation.** iRT's LMS will record the amount of time that users spend on the website components and the specific components that were reviewed.

**Consumer Satisfaction Questionnaire (CSQ)** will assess satisfaction for each of the three components of the website in terms of: (1) content (e.g., The information in the Spotlights was interesting to me.); (2) format (e.g., I liked that there were games and activities I could play in the Investigations.); (3) usability (e.g., I could figure out how to make the Comics work.). Overall quality will also be assessed (e.g., I would recommend this resource to a friend that was considering participating in research.). Participants will rate each item on a 5-point Likert scale (1 = Strongly Disagree, 2 = Disagree, 3 = Undecided, 4 = Agree, and 5 = Strongly Agree).

## Statistical Analysis Plan

**Preliminary Analyses.** Chi-squared analyses will be used to examine if the randomization process produced equivalent groups between the wait-list control and intervention groups with respect to gender, race, ethnicity, health status, and SES. A t-test will be used to examine if the randomization process produced equivalent groups between the wait-list control and intervention groups with respect to age. If any of these demographical variables are found to differ significantly between the two groups, they will be included as covariates in the main analyses. Finally, the outcome variables will be examined to see if the values are normally distributed.

*Main Analyses.* Intent-to-treat (ITT) analyses will focus on examining the feasibility of *DKIN: Teen* for making positive changes in youth outcomes related to participation in clinical trials. A series of single factor, condition (intervention, wait-list control) random effects ANOVA models will be used to examine if using *DKIN: Teen* impacts the posttest 1) knowledge, 2) attitudes, 3) beliefs, 4) self-efficacy, 5) fears related to participation as well as likelihood to participate and 6) likelihood that fears would prevent participation. Pretest scores for each outcome will be included as predictor variables; therefore, outcome variable means will be adjusted posttest scores. Because this study is not powered to find significant differences (i.e., p-values) between groups, small or larger effect sizes (Cohen's d) will be emphasized during interpretation as evidence of feasibility.

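### Age is not a randomisation factor and enters the models only after a significant baseline t-test; it should be a pre-specified covariate whatever the test shows

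*Combined protocol and SAP*

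**What the plan says.** Under Methods (Sample and Recruitment), youth must "be between the ages of 12 and 17 years". The same section aims for arms with "about equal amounts of boys and girls as well as healthy youth and youth with varying chronic diseases/disorders", and for racial and ethnic diversity; age is not mentioned. Under Methods (Procedure), randomisation is done by "stratifying based upon gender (boy/girl/non-binary), race/ethnicity (white/nonwhite), and health status (healthy/chronic illness"; again age is absent.

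The Statistical Analysis Plan (Preliminary Analyses) then states: "A t-test will be used to examine if the randomization process produced equivalent groups" with respect to age. The consequence is a single rule for age and the other demographic variables: "If any of these demographical variables are found to differ significantly between the two groups, they will be included as covariates".

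Under Main Analyses, each model already contains the pretest score of its own outcome. That paragraph also says "Because this study is not powered to find significant differences (i.e., p-values) between groups", and takes a Cohen's d of at least small size as the evidence of feasibility. Neither the sample size nor the significance level of the baseline test is given; the Design section says only "A small randomized controlled trial design will be conducted online at two time points".

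**The concern.** The t-test is asked to do two jobs and suits neither.

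- **Showing that the arms are alike in age.** A non-significant result in a small trial is weak evidence of similarity. The plan itself discounts significance testing at this size when it comes to the outcomes.
- **Choosing the model.** The reason to adjust for age is that it predicts the outcome. A test of the difference between arms does not address that. With sound randomisation, any difference in age is due to chance, so the test is significant at its nominal rate and age is left out of nearly all trials, whether or not it matters.

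At stake is the adjusted d, on which the interpretation rests. Knowledge, self-efficacy and fear of procedures could plausibly vary over ages 12 to 17. If age predicts posttest beyond pretest, a chance age difference that misses significance moves d, and the precision that age could supply is lost. The covariate set is also settled only after the data have been seen.

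**Working it through.** The plan gives no figure to reproduce: sample size, significance level, age SD and age-outcome relation are all absent.

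**Assumptions.** Total N of 60, 80 or 120; 1:1 allocation; two-sided 0.05; outcome SD of 1; residual age slope b (SD of posttest per SD of age, given pretest) of 0.1, 0.2 or 0.3; pretest slope 0.6; age uncorrelated with pretest.

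**Step 1: largest age difference left unadjusted.** In SD units it is t(0.975, N-2) × 2/√N. The typical (root-mean-square) chance difference is 2/√N.

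| Total N | t | 2/√N | Largest unadjusted |
|---|---|---|---|
| 60 | 2.002 | 0.258 | 0.517 |
| 80 | 1.991 | 0.224 | 0.445 |
| 120 | 1.980 | 0.183 | 0.362 |

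The answer moves with N: 0.64 SD at 20 per arm and 0.28 SD at 100 per arm.

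**Step 2: shift in adjusted d.** Shift = b × imbalance.

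| Total N | Worst case, b = 0.2 | Worst case, b = 0.3 | Typical, b = 0.2 | Typical, b = 0.3 |
|---|---|---|---|---|
| 60 | 0.10 | 0.16 | 0.05 | 0.08 |
| 80 | 0.09 | 0.13 | 0.04 | 0.07 |
| 120 | 0.07 | 0.11 | 0.04 | 0.05 |

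A simulation with 40 per arm, an age imbalance fixed at 0.45 SD and a pretest slope of 0.5 gave shifts of 0.08-0.09 at b = 0.2 and 0.12-0.13 at b = 0.3 with pretest adjustment only. With age added, the mean shift was about 0 (-0.002 to 0.009 over slopes 0.1 to 0.4).

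**Step 3: precision.** Residual variance with age in the model is r = 1 - 0.6² - b². Estimating the age slope inflates the variance by about k = 1/(N-4). The 5% of trials that the test flags hold a share q = 0.05 + 2 × 1.96 × φ(1.96) = 0.05 + 0.229 = 0.279 of the imbalance variance, φ being the standard normal density. Apart from a common factor:

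- always adjusting: r(1 + k)
- stated rule: r(1 + qk) + b²(1 - q)

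For N = 80 and b = 0.2: r = 0.60 and k = 1/76 = 0.0132. Always adjusting gives 0.6079. The stated rule gives 0.6022 + 0.0288 = 0.6310. The reduction is 1 - 0.6079/0.6310 = 3.7%.

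| b | Formula, N = 60 / 80 / 120 | Simulation, N = 60 / 80 / 120 |
|---|---|---|
| 0.1 | -0.1% / 0.2% / 0.5% | between -0.8% and 0.3% |
| 0.2 | 3.3% / 3.7% / 4.0% | 4.2% / 3.1% / 4.4% |
| 0.3 | 9.4% / 9.7% / 10.0% | 9.4% / 9.6% / 10.6% |

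The simulation used 6,000 trials per setting with age uniform over 12 to 17 completed years. Repeat runs put the b = 0.3 reduction at about 8-11%. The age test was significant in about 5% of simulated trials, and the estimate under the stated rule had mean error near zero.

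**The case against.** The strongest reply is that the consequence is small, and most of its parts stand.

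- **No bias.** Randomisation balances age in expectation, and the stated rule gives an estimate centred on the truth. A reader might infer that d is systematically distorted; nothing in the documents supports that.
- **The pretest already does much of the work.** The same outcome is measured about a week earlier and is in the model, so an age effect on level is largely absorbed. A reader might infer that the whole age effect passes into d; only the residual part does. If age correlates r with both pretest and posttest, and the pretest slope is 0.6, the residual slope is r - 0.6r = 0.4r. A slope of 0.2 then needs r = 0.5, and 0.3 needs r = 0.75. Otherwise age must predict gain, for example through older youth learning more from the site, on which the documents give no figure.
- **The imbalance is a worst case on an assumed N.** A reader might take an undetected difference of 0.4-0.5 SD as a property of this trial. It is the threshold for about 32-49 per arm only. The chance that a difference of at least 0.4 SD escapes the test is about 8% at 30 per arm, 3% at 40 and nil from 50.
- **Other noise is larger.** The standard error of the adjusted difference is about √(4 × 0.64/N), or 0.21, 0.18 and 0.15 at N of 60, 80 and 120, against a typical age-related shift of 0.04-0.08.
- **The rule is wider than age.** SES is also unstratified and falls under the same rule, so a change for age alone leaves the rule in place for SES.

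These points limit the size. They do not make a significance test a sound way to choose a covariate or to show equivalence, and no other section removes the rule.

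**Conclusion.** The point holds as a modest, inexpensive improvement. The plan leaves age out unless a test that is significant in about 5% of soundly randomised trials happens to flag it, and a non-significant result cannot show that the arms are equivalent.

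At total N of 60 to 120, an imbalance of up to about 0.36-0.52 SD would go unadjusted. At residual slopes of 0.2-0.3 that is a worst-case shift in adjusted d of about 0.07-0.16 and a typical one of about 0.04-0.08, in either direction. Set against a d of 0.2 as the conventional meaning of small (the plan gives no cut-off), this could matter to the interpretation near the boundary, but it is one component of a larger chance error. The precision gain is about 3-4% of variance at slope 0.2, about 8-11% at 0.3 and essentially nil at 0.1.

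Sample size, allocation ratio, significance level and slopes are all assumptions. The criticism of the rule itself does not depend on them.

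**What to change.** In Main Analyses, name age (in years, as a linear term) as a covariate beside the pretest score in every model, regardless of the baseline comparison. In Preliminary Analyses, delete the t-test on age and its equivalence reading, and report mean age by arm with a standardised difference.

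The cost is one line in the plan and one degree of freedom per model. Age is already needed for eligibility and for the planned comparison. If age proves weakly predictive, the loss of precision is negligible: at slope 0.1 the change in variance stayed within 1% either way at the sizes examined.

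### The main models leave out the factors used to stratify randomisation and admit them only after a significant baseline test (minor)

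*Combined protocol and SAP*

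**What the plan says.** The Study Protocol (Methods, Procedure) names three stratification factors: "Participants will be randomized, stratifying based upon gender (boy/girl/non-binary), race/ethnicity (white/nonwhite), and health status (healthy/chronic illness"). It does not say how arms are balanced within strata; no blocks, block size or other method is given.

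The Statistical Analysis Plan (Main Analyses) specifies: "A series of single factor, condition (intervention, wait-list control) random effects ANOVA models will be used". One covariate is fixed in advance: "Pretest scores for each outcome will be included as predictor variables".

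Other variables are handled under Preliminary Analyses. Chi-squared tests compare the arms "with respect to gender, race, ethnicity, health status, and SES", and a t-test compares age. The rule that follows is: "If any of these demographical variables are found to differ significantly between the two groups, they will be included as covariates". No significance threshold is stated. Race and ethnicity are tested as separate variables; the white/nonwhite factor used for stratification is not itself tested.

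Main Analyses also limits what is at stake: "Because this study is not powered to find significant differences (i.e., p-values) between groups". Effect sizes "will be emphasized during interpretation as evidence of feasibility".

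**The concern.** Design and analysis do not match. Stratification exists to prevent imbalance on three factors, yet the analysis lets those factors in only when they are imbalanced. The consequence depends on an allocation method that the documents leave open.

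- **Balanced within strata (for example by blocks).** The rule is close to inert for gender and health status. The model then treats between-strata variation as noise, although the design has largely removed it from the comparison. Standard errors come out too large to the extent that the strata predict posttest beyond pretest.
- **Unrestricted within strata.** Standard errors are right, but chance imbalance rather than prognostic value decides which model is fitted, and precision is lost if the factors are prognostic.

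At stake are the accuracy of any standard error, interval or p-value that is reported, and whether the model behind the adjusted means is known in advance.

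**Working it through.** **Inputs.** From the documents: 3 × 2 × 2 = 12 strata, a model with condition and pretest, and the baseline-test rule. They give no sample size, allocation method, category frequencies or prognostic strength, so there is no stated figure to reproduce. Assumed: N = 40, 60 or 80; 1:1 allocation; 4% non-binary, 40% nonwhite, 50% chronic illness; pre-post correlation 0.6; Pearson chi-squared at 0.05. The strata are taken to explain a share R² of posttest variance left after pretest, split evenly over the three factors. The plan says random effects but names none, so condition and pretest are fixed terms. There were 20,000 simulated trials per setting (Monte Carlo error about 0.5% on an SD).

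**1. How often the rule admits a stratifier**

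- Blocks of 2 or 4 within strata: at most 0.02% of trials. Blocks of 6: 0.2%. Blocks of 8: 0.7%.
- These rates treat white/nonwhite as the tested variable. The plan tests race and ethnicity instead. With an assumed five-category race variable and N of 40-200 (3,000 trials per setting), race fired in about 1-2.5% and ethnicity in about 2.5-4% under blocking.
- Simple allocation: at least one of the three factors in 13.2-14.5%; smaller repeat runs put this at 12-15%.

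**2. Balanced allocation, strata omitted.** With perfect balance, model SE / true SD ≈ 1/√(1 − R²), and the actual size of a nominal 5% test ≈ 2[1 − Φ(1.96/√(1 − R²))].

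| R² | Formula SE ratio | Simulated SE/SD, blocks of 4, N = 40 / 60 / 80 |
|---|---|---|
| 0 | 1.000 | 0.994 / 1.001 / 0.999 |
| 5% | 1.026 | 1.017 / 1.012 / 1.017 |
| 10% | 1.054 | 1.038 / 1.041 / 1.047 |
| 20% | 1.118 | 1.081 / 1.096 / 1.109 |

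The simulated excess is smaller because incomplete blocks leave some imbalance. Across other block sizes, effects placed in one factor or spread over the 12 cells, and repeat runs of 4,000 trials, the excess is about 2-7% at 10% and 6-11% at 20%.

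- Type I error at a nominal 5%: 3.9-4.1% at 10% and 2.8-3.4% at 20% (formula 3.9% and 2.8%). With the strata included: 4.7-5.1%.
- Example, N = 80, R² = 20%, blocks of 4: omitted, SE 0.1798 against SD 0.1621, ratio 1.109; included, 0.1613 against 0.1606, ratio 1.004.
- True precision hardly moves: the SD with strata included is 0.987-1.010 times the SD without.

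**3. Simple allocation.** SE/SD is 0.986-1.005 and type I error 4.8-5.3%, so there is no excess. Against the current rule, always including the strata changes the true SD by +1.4 to +2.7% at R² = 0, −0.9 to −2.5% at 10% and −5.7 to −7.1% at 20%. Example, N = 80, R² = 20%: 0.1672 included against 0.1790 under the rule (0.1672/0.1790 = 0.934) and 0.1819 with strata never included (0.1672/0.1819 = 0.919). The gain is thus about 1-3% at 10% and 6-8% at 20%.

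**4. Variables that are not stratified.** Two independent 5% tests, as for SES and age, would change the model in 1 − 0.95² = 9.8% of trials. All six listed tests, if independent, would do so in 1 − 0.95⁶ = 26.5%.

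**The case against.** The strongest reply is that no planned result is shown to be harmed. The estimate is unbiased, the error under balanced allocation is conservative, p-values are set aside in favour of Cohen's d, and no interval is planned. The size also rests on an input that the documents do not supply: nothing in them shows that gender, white/nonwhite or health status predicts posttest once the same measure's pretest is in the model. At shares of 5% or less the net gain is near zero. All of this stands, and it caps the point at minor. It does not supply a reason for the rule: the plan still reports adjusted means, so the adjusting variables should be fixed beforehand.

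Three stronger readings are tempting and not supported.

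- A reader might infer that the baseline rule almost never fires at all. That fits gender and health status under balanced allocation. It does not fit race and ethnicity, which stratification controls only in part, nor SES and age, which are not stratified.
- A reader might take blocked allocation as given. The word for stratifying makes balance within strata the natural reading, but no method is stated. The aim of similar groups, "Efforts will be made to ensure that the intervention and wait-list control groups have about equal amounts of boys and girls", sits under Sample and Recruitment and may describe recruitment quotas, so it adds little.
- A reader might infer that the omission favours the intervention. Under balanced allocation it makes tests and intervals too cautious; under unrestricted allocation it leaves them correct.

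A rule for a sparse non-binary level also depends on the allocation. That is true, but it uses no outcome data and can be written down in advance.

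**Conclusion.** The point holds as a minor mismatch between design and analysis. It is certain from the text that the stratification factors are not pre-specified in the main models and enter only through baseline tests. The numerical consequence is conditional: standard errors about 2-7% too large at an assumed 10% share and 6-11% at 20% if arms are balanced within strata; no standard-error excess, but a model chosen by chance imbalance in about 12-15% of trials, if they are not. These figures rest on the assumed sample size, category frequencies, allocation method and prognostic share. How Cohen's d is standardised is a separate matter and forms no part of this point.

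**What to change.** State in the Statistical Analysis Plan that:

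1. Every main model includes gender, white/nonwhite and health status as fixed main effects, with condition and that outcome's pretest score, whatever the baseline comparisons show.
2. Significance-triggered entry is dropped for all variables, including SES and age. The baseline comparisons stay as description, and any further covariate that is wanted is named in advance.
3. If all non-binary participants fall in one arm, that level is pooled for the model only, by a rule fixed beforehand, and no one is excluded. One such rule pools it with the larger of the boy and girl groups among all randomised youth, girl if equal. Under blocks this would apply in 43-48% of trials at N = 40 and 22-28% at N = 80, so the rule is needed.

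**Cost.** A few sentences and no new data. The terms use up to 2 + 1 + 1 = 4 residual degrees of freedom. If the strata are not prognostic, intervals widen relative to a model without them by 1.1-1.4% at N = 40 and 0.4-0.5% at N = 80 under balanced allocation, and by 4.8% and 2.3% under simple allocation. If effects are specific to the 12 cells, main effects remove only about half of the excess (at a 20% share, SE/SD falls from 1.08-1.09 to 1.03-1.04).

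### The only evidence of feasibility the SAP names is a small or larger Cohen's d, and the website-usage and satisfaction data have no planned analysis

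*Combined protocol and SAP*

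**What the plan says.** The Objectives section of the protocol opens the aim with "The main objective of the study is to examine the feasibility of" DKIN: Teen and continues "and its impact on adolescents' knowledge about pediatric clinical trials", followed by self-efficacy, attitudes and beliefs, and fears. Feasibility and impact are both parts of the main objective.

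The Main Analyses paragraph of the SAP has the intention-to-treat analyses examine feasibility "for making positive changes in youth outcomes related to participation in clinical trials". The models compare the two conditions on posttest outcomes with the pretest score as a predictor. The paragraph then states that "this study is not powered to find significant differences (i.e., p-values) between groups", and for that reason "small or larger effect sizes (Cohen's d) will be emphasized during interpretation as evidence of feasibility".

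Two other data sources are described under Measures. Under Fidelity of Implementation, the learning management system (LMS) logs time spent and which components were viewed. The CSQ rates content, format, usability and overall quality. Under Procedure, access is followed closely enough to trigger "automatic email reminders from the study management system if their teen has not completed the questionnaires or has not accessed" the site, with a call or check-in email from staff if there is still no response. The SAP mentions neither the LMS nor the CSQ.

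**The concern.** A between-arm effect size and feasibility answer different questions. Cohen's d estimates how far outcomes differ between the arms. It cannot show how many youth opened the site, how much they reviewed, or whether they found it workable. Exposure will vary by design, because youth may review as much or as little as they choose within the week.

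Two things are at stake. First, a chance difference in a small study could be reported as evidence that the website is feasible, with no interval to show how uncertain it is. Second, the data that bear on use and usability would be summarised without a plan, if at all. Denominators and groupings would then be chosen after the data are seen, although they can change the answer: access among those randomized differs from access among those actually sent the link.

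**Working it through.** **Reading the text.** The SAP has two parts. Preliminary Analyses covers baseline balance (chi-squared tests, a t-test for age) and a normality check. Main Analyses covers the pretest-adjusted comparisons and the sentence on effect sizes. Setting these against Measures:

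| Data collected | Where described | Planned analysis |
|---|---|---|
| Knowledge, attitudes, beliefs, self-efficacy, fears | Measures | Yes: adjusted comparison, Cohen's d |
| LMS time and components | Procedure; Fidelity of Implementation | None |
| CSQ ratings | Procedure; CSQ | None |

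LMS monitoring and non-access reminders are study conduct, not analysis. For the LMS and CSQ data there is no summary statistic, denominator or criterion.

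**Illustration of how imprecise d is.** There is no figure of the plan's to reproduce: the documents give no sample size (the trial is only called small), no number for small, no standardiser for d and no correlations. Assumptions: equal arms of n; true effect zero; small means d ≥ 0.2 in the favourable direction; pretest–posttest correlation r = 0.6 where needed.

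The standard error of d depends on the standardiser:

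- residual SD in the adjusted model (or an unadjusted comparison): SE = √(2/n)
- raw SD in the adjusted model: SE = √((1 − r²)·2/n) = √(0.64·2/n)

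The chance that one outcome reaches 0.2 is P(t > 0.2/SE), here with 2n − 2 degrees of freedom:

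| n per arm | SE, residual SD | Chance | SE, raw SD | Chance |
|---|---|---|---|---|
| 30 | 0.258 | 0.22 | 0.207 | 0.17 |
| 50 | 0.200 | 0.16 | 0.160 | 0.11 |
| 100 | 0.141 | 0.08 | 0.113 | 0.04 |

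The SAP numbers six outcomes (the fifth item can be read as two) and does not say how many would need to show a small effect. For six outcomes correlated 0.5 with each other (equicorrelated normal), the chance under no effect is:

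| Requirement | n = 30 (raw to residual SD) | n = 50 (raw to residual SD) |
|---|---|---|
| At least one of six | 0.46–0.55 | 0.33–0.45 |
| At least four of six | 0.08–0.12 | 0.04–0.08 |
| All six | 0.01–0.02 | 0.005–0.01 |

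With correlations from 0.3 to 0.7, the at-least-one figure runs from 0.27 to 0.64 over the same sample sizes.

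**Interval for an observed adjusted d of 0.2** (raw SD, r = 0.6), as 0.2 ± 1.96·SE:

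- n = 30: 0.2 ± 0.405, or −0.20 to 0.60
- n = 50: 0.2 ± 0.314, or −0.11 to 0.51
- n = 100: 0.2 ± 0.222, or −0.02 to 0.42

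All three intervals include zero.

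**The case against.** The strongest reply is that the SAP uses feasibility in a sense of its own: early promise of effect, openly stated alongside the admission that the study is not powered. On that view the dispute is partly about a label. The Objectives section states one main objective, not two formally separate aims. The LMS data are labelled fidelity, and the CSQ is described as feedback on the website. This stands in part. The documents do not call either source a feasibility measure, so a reader who infers that designated feasibility endpoints were dropped from the analysis goes further than the text allows. The reply does not remove the gap. Impact is named alongside feasibility in the objective, the SAP leaves feasibility with no content beyond impact, and the data on use and usability go unanalysed under any label.

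A reader might also infer that the SAP sets a pass/fail test on d. It does not: effect sizes are to be emphasised in interpretation, which leaves room for other evidence. The point is only that no other evidence is planned.

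Nor should the at-least-one-of-six figure be taken as the trial's false-positive rate. The documents never say one outcome suffices, and stricter readings give much smaller chances.

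Finally, about one hour is the estimated time for full completion, and youth are told they may review as much as they want. Shorter use is not by itself a failure of feasibility.

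**Conclusion.** The point holds as a gap between the objective and the analysis. The only feasibility evidence the SAP names is a point estimate that does not measure access, amount used or usability, and the data that bear on those questions have no planned analysis. This rests on the text and needs no assumed number.

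The arithmetic is illustrative. Under no true effect, one outcome shows d ≥ 0.2 about 11–22% of the time at 30–50 per arm and 4–8% at 100 per arm. At 30–50 per arm with outcomes correlated 0.5, at least one of six does so 33–55% of the time and at least four of six 4–12%. These figures depend on the assumed sample size, cut-off, standardiser and correlations.

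The documents do not support reading this as a flaw in the randomized comparison. The intention-to-treat contrast is unaffected and can be interpreted without usage data, although usage would help explain a small or null d. The change should be made, because it alters what the trial can conclude about feasibility at little cost.

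**What to change.** 1. In Main Analyses, reword the opening sentence and the last sentence together. Report the pretest-adjusted group difference and Cohen's d for every outcome, with 95% confidence intervals and a stated standardiser, as preliminary estimates of impact. Remove the description of d as evidence of feasibility, or call it preliminary evidence of promise.

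2. State what feasibility means and which collected data answer it, and add a short descriptive section with 95% confidence intervals:
   - Intervention arm: numbers randomized, completing pretest, sent access and accessing the site. Give access as a proportion of those randomized and of those sent access, because access instructions follow the pretest link. Describe it as access with reminders and staff contact.
   - Distributions of time spent and components reviewed. Mention that the site "is expected to take about 1 hour to fully complete" only as the estimate for full completion, and note that youth may review as much as they want.
   - CSQ summaries for content, format, usability and overall quality, with respondents out of those randomized. Keep the optional wait-list responses separate, since they follow later access.
   - Posttest completion by arm.

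3. Set any feasibility criterion before usage, CSQ or outcome data are examined. Staff monitor usage during the study, so a criterion set only before the outcome data are seen could still be post hoc. Otherwise, state that the section is descriptive.

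The cost is two reworded sentences, a definition of feasibility and a few tables from data already collected. The downside is that the feasibility conclusion may be less favourable than one drawn from effect sizes.
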